11.7. Follow-up of AEs and SAEs

After the initial AE/SAE report, the Principal Investigator is required to proactively follow each event at subsequent visits/contacts until the event resolves. All SAEs and AEs will be followed until resolution, or until the condition stabilizes or until the participant is lost to follow-up. Where necessary, repeated laboratory testing should be

requested to confirm resolution. Ongoing AEs where no further information is likely to be available may be closed after consultation between the Sponsor and Medical Monitor.

11.8. Regulatory Reporting Requirements for SAEs

Prompt notification by the Investigator to the Sponsor of SAEs/adverse event of special interest (AESIs) is essential so that legal obligations and ethical responsibilities towards the safety of subjects and the safety of a product under clinical investigation are met.

The Sponsor has a legal responsibility to notify both the local regulatory authority and other regulatory agencies about the safety of a product under clinical investigation. The Sponsor will comply with country specific regulatory requirements relating to safety reporting to the regulatory authority, IRB/IEC and Investigator.

Investigator safety reports are prepared for suspected unexpected serious adverse reactions (SUSARs) according to local regulatory requirements and are forwarded to the Investigators in accordance with local regulations.

The Investigator who receives an Investigator safety report describing a SAE(s)/AESI(s) or other specific safety information (e.g., summary or listing of SAEs) from the Sponsor will file it with the IB and will notify the IRB/IEC, as appropriate according to local requirements.

11.9. Overdose

Overdose is less likely in a study where the drug is administered within a clinical unit by a healthcare provider. If there are no symptoms of an overdose, it should be recorded as a protocol deviation. Overdose with symptoms should be recorded as an AE or SAE, as appropriate.

12. PREGNANCY REPORTING

All female participants will be tested for pregnancy prior to study drug dosing. Participants testing positive for pregnancy will be ineligible for study participation.

Any pregnancies in a participant, or the partner of a participant, between the time of informed consent and study termination must be reported to the Sponsor within 24 hours of learning of the pregnancy. Information on the status and health of the mother, the pregnancy and its outcome, and the child will be recorded on the form provided. In case of a partner pregnancy, the partner of the study participant will be asked to sign a partner pregnancy consent form in order to collect pregnancy and outcome information. Information on the status of the mother and child will be forwarded to the Sponsor. Follow-up will be done for the newborn at birth and 12 months of age with parental consent. Any premature termination of the pregnancy will be reported. Complications of the pregnancy affecting either the mother or fetus that meet seriousness criteria (Section 11.2) should be reported as an SAE. A planned abortion is not considered an SAE.

13. RESPONSIBILITIES

13.1. Principal Investigator Responsibilities

13.1.1. Good Clinical Practice (GCP)

The Principal Investigator will ensure that this study is conducted in accordance with the principles of the “Declaration of Helsinki” (as amended in Edinburgh, Tokyo, Venice, Hong Kong, and South Africa), International Conference on Harmonisation (ICH) guidelines, or with the laws and regulations of the country in which the research is conducted, whichever affords the greater protection to the study participant. For studies conducted under a United States IND, the Principal Investigator will ensure that the basic principles of “Good Clinical Practice,” as outlined in 21 Code of Federal Regulations (CFR 312), subpart D, “Responsibilities of Sponsors and Investigators,” 21 CFR, part 50, 1998, and 21 CFR, part 56, 1998, are adhered to. These standards are consistent with the requirements of the European Community Directive 2001/20/EC.

Since this is a “covered” clinical trial, the Principal Investigator will ensure that 21 CFR, Part 54, 1998, is adhered to; a “covered” clinical trial is any “study of a drug or device in humans submitted in a marketing application or reclassification petition participant to this part that the applicant or FDA relies on to establish that the product is effective (including studies that show equivalence to an effective product) or that make a significant contribution to the demonstration of safety.” This requires that Principal Investigators and all sub-investigators must provide documentation of their financial interest or arrangements with the Sponsor, or proprietary interests in the drug being studied. This documentation must be provided before participation of the Principal Investigator and any sub-investigator. The Principal Investigator and sub-investigator agree to notify the Sponsor of any change reportable interests during the study and for one year following completion of the study. Study completion is defined as the date that the last participant has completed the protocol defined activities.

13.1.2. Institutional Review Board (IRB)/Independent Ethics Committee (IEC) Approval

This protocol and any accompanying material to be provided to the participant (such as informed consent form, advertisements, participant information sheets, or descriptions of the study used to obtain informed consent) will be submitted by the Principal Investigator to an IRB or IEC. Approval from the IRB or IEC must be obtained before starting the study and should be documented in a letter to the Principal Investigator specifying the protocol number, protocol version, protocol date, documents reviewed, and date on which the committee met and granted the approval.

Any modifications made to the protocol after receipt of IRB or IEC approval must also be submitted to the IRB or IEC for approval before implementation.

The investigator will be responsible for the following:

- Providing written summaries of the status of the study to the IRB/IEC on an annual basis or more frequently in accordance with the requirements, policies, and procedures established by the IRB/IEC.
- Notifying the IRB/IEC of SAEs or other significant safety findings as required by procedures established by the IRB/IEC.

13.1.3. Informed Consent

The Principal Investigator or designee is responsible for obtaining written informed consent from each individual participating in this study after adequate explanation of the aims, methods, objectives, and potential hazards of the study and before undertaking any study-related procedures. The Principal Investigator must utilize an IRB or IEC-approved consent form for documenting written informed consent. Each informed consent will be appropriately signed and dated by the participant and the person obtaining consent.

Participants must be re-consented to continue their participation in the study if a protocol amendment is made that substantially alters the study design or the potential risks or burden to the participant.

13.1.4. Confidentiality

The Principal Investigator must assure that participants' anonymity will be strictly maintained and that their identities are protected from unauthorized parties. Only participant number (i.e., not names) and month and year of birth (as allowed) should be recorded on any form or biological sample submitted to the Sponsor, IRB or IEC, or laboratory. The Principal Investigator must keep a screening log showing codes, names, and addresses for all participants screened and for all participants enrolled in the trial.

The Principal Investigator must keep a screening log showing codes, names, and addresses for all participants screened and for all participants enrolled in the trial.

The Principal Investigator agrees that all information received from the Sponsor, including but not limited to the IB, this protocol, eCRFs, the investigational new drug, and any other study information, remain the sole and exclusive property of the Sponsor during the conduct of the study and thereafter. This information is not to be disclosed to any third party (except employees or agents directly involved in the conduct of the study or as required by law) without prior written consent from the Sponsor. The Principal Investigator further agrees to take all reasonable precautions to prevent the disclosure by any employee or agent of the study site to any third party or otherwise into the public domain.

13.1.5. Study Files and Retention of Records

The Principal Investigator must maintain adequate and accurate records to enable the conduct of the study to be fully documented and the study data to be subsequently

verified. These documents should be classified into at least the following two categories: (1) Investigator's study file, and (2) participant clinical source documents.

The Investigator's study file will contain the IB, protocol/amendments, eCRF and query forms, IRB or IEC and governmental approval with correspondence, informed consent, drug records, staff curriculum vitae and authorization and training forms, and other appropriate documents and correspondence.

The required source data should include the following for each participant:

- participant identification (name, month and year of birth, gender);
- documentation that participant meets eligibility criteria, i.e., history, physical examination, and confirmation of diagnosis (to support inclusion and exclusion criteria);
- participation in trial (including trial number);
- trial discussed and date of informed consent;
- dates of all visits;
- documentation that protocol specific procedures were performed;
- results of efficacy parameters, as required by the protocol;
- start and end date (including dose regimen) of trial medication (preferably drug dispensing and return should be documented as well);
- record of all AEs and other safety parameters (start and end date, and preferably including causality and intensity);
- concomitant medication (including start and end date, dose if relevant; dose changes should be motivated);
- date of trial completion and reason for early discontinuation, if applicable.

All clinical study documents must be retained by the Principal Investigator until at least 2 years after the last approval of a marketing application in an ICH region (i.e., United States, Europe, or Japan) and until there are no pending or contemplated marketing applications in an ICH region; or, if no application is filed or if the application is not approved for such indication, until 2 years after the investigation is discontinued and regulatory authorities have been notified. The Principal Investigator may be required to retain documents longer if required by applicable regulatory requirements, by local regulations, or by an agreement with the Sponsor. The Principal Investigator must notify the Sponsor before destroying any clinical study records.

Should the Principal Investigator wish to assign the study records to another party or move them to another location, the Sponsor must be notified in advance.

If the Principal Investigator cannot guarantee this archiving requirement at the study site for any or all of the documents, special arrangements must be made between the Principal Investigator and the Sponsor to store these in sealed containers outside of the site so that they can be returned sealed to the Principal Investigator in case of a regulatory audit. When source documents are required for the continued care of the participant, appropriate copies should be made for storage outside of the site.

Biological samples at the conclusion of this study may be retained in storage by the Sponsor for a period up to 10 years for purposes of this study.

13.1.6. Electronic Case Report Forms (eCRF)

For each participant enrolled, an eCRF must be completed and signed by the Principal Investigator or sub-investigator (as appropriate) within a reasonable time period after data collection. This also applies to records for those participants who fail to complete the study (even during the screening period if an eCRF was initiated). If a participant withdraws from the study, the reason must be noted on the eCRF. If a participant is withdrawn from the study because of a treatment-limiting AE, thorough efforts should be made to clearly document the outcome.

13.1.7. Drug Accountability

The Principal Investigator or designee (i.e., pharmacist) is responsible for ensuring adequate accountability of all used and unused investigational product. This includes acknowledgment of receipt of each shipment of study product (quantity and condition), participant dispensing records, and returned or destroyed study product. Dispensing records will document quantities received from the Sponsor and quantities dispensed to participants, including lot number, date dispensed, participant identifier number, and the initials of the person dispensing the medication.

At study initiation, the monitor will evaluate the site's standard operating procedure for investigational medicinal product disposal/destruction in order to ensure that it complies with the Sponsor requirements. Drug may be returned or destroyed on an ongoing basis during the study as appropriate. At the end of the study, following final drug inventory reconciliation by the monitor, the study site will return all unused investigational medicinal product supplies. If the site cannot meet the Sponsor's requirements for disposal, arrangements will be made between the site and the Sponsor or its representative for destruction or return of unused investigational medicinal product supplies.

All drug supplies and associated documentation will be periodically reviewed and verified by the study monitor over the course of the study.

13.1.8. Inspections

The Principal Investigator should understand that source documents for this trial should be made available to appropriately qualified personnel from the Sponsor or its

representatives, to IRBs or IECs, or to regulatory authority or health authority inspectors.

13.1.9. Protocol Compliance

The Principal Investigator is responsible for ensuring the study is conducted in accordance with the procedures and evaluations described in this protocol.

13.2. Sponsor Responsibilities

13.2.1. Protocol Modifications

Protocol modifications, except those intended to reduce immediate risk to study participants, may be made only by the Sponsor.

13.2.2. Study Report and Publications

A clinical study report will be prepared and provided to the regulatory agency(ies). The Sponsor will ensure that the report meets the standards set out in the ICH Guideline for Structure and Content of Clinical Study Reports (ICH E3). Note that an abbreviated report may be prepared in certain cases.

13.2.3. Posting of Information on Publicly Available Clinical Trial Registers

Study information from this protocol will be posted on publicly available clinical trial registers within 21 days of enrollment of the first participant. Results will be posted as required.

13.3. Joint Investigator/Sponsor Responsibilities

13.3.1. Access to Information for Monitoring

In accordance with ICH Good Clinical Practice guidelines, the study monitor must have direct access to the Principal Investigator's source documentation in order to verify the data recorded in the eCRFs for consistency.

The monitor is responsible for routine review of the eCRFs at regular intervals throughout the study to verify adherence to the protocol and the completeness, consistency, and accuracy of the data being entered on them. The monitor should have access to any participant records needed to verify the entries on the eCRFs. The Principal Investigator agrees to cooperate with the monitor to ensure that any problems detected in the course of these monitoring visits are resolved.

13.3.2. Access to Information for Auditing or Inspections

Representatives of regulatory authorities or of the Sponsor may conduct inspections or audits of the clinical study. If the Principal Investigator is notified of an inspection by a regulatory authority the Principal Investigator agrees to notify the Sponsor medical monitor immediately. The Principal Investigator agrees to provide to representatives of a regulatory agency or the Sponsor access to records, facilities, and personnel for the effective conduct of any inspection or audit.

13.3.3. Study Discontinuation

The Sponsor reserves the right to terminate the study at any time. Should this be necessary, the Sponsor will arrange discontinuation procedures and notify the appropriate regulatory authority (ies), IRBs, and IECs. In terminating the study, the Sponsor and the Principal Investigator will assure that adequate consideration is given to the protection of the participants' interests.

Reasons for stopping the study may include but are not limited to:

- New evidence that, in the opinion of the sponsor, makes continuation of the study unnecessary or unethical
- The sponsor discontinues development of RVT-1401
- Insufficient patient enrollment

15. APPENDICES

15.1. Appendix 1: Abbreviations and Trademarks

Abbreviations

ADA	Anti-drug antibody
ADCC	Antibody dependent cell mediated cytotoxicity
AE	Adverse event
AESI	Adverse event of special interest
AIHA	Autoimmune hemolytic anemia
ALT	Alanine aminotransferase
AST	Aspartate aminotransferase
BMI	Body mass index
BUN	Blood urea nitrogen
CI	Confidence intervals
CLL	Chronic lymphocytic leukemia
CO ₂	Carbon dioxide
CPK	Serum creatine phosphokinase
CTCAE	Common Terminology Criteria for Adverse Events
DAT	Direct antiglobulin test
ECG	Electrocardiogram
eCRF	Electronic case report form
FcRn	fully human anti-neonatal FC receptor
FDA	U.S. food and drug administration
FSH	Follicle stimulating hormone
GCP	Good Clinical Practice
GGT	Gamma glutamyltransferase
Hb	Hemoglobin
HBV	Hepatitis B virus
HCV	Hepatitis C virus
HIV	Human immunodeficiency virus
IB	Investigator's brochure
ICF	Informed consent form
ICH	International conference on harmonisation
IEC	Independent ethics committee
IgA	Immunoglobulin A
IgG	Immunoglobulin G
IgM	Immunoglobulin M
IND	Investigational new drug
INR	International normalized ratio
IP	Investigational product
IRB	Institutional review board
ITP	Idiopathic thrombocytopenia purpura
ITT	Intent to treat
IUD	Intrauterine device

IUS	Intrauterine system
IV	Intravenous
IVIG	Intravenous immunoglobulin
IXRS	Interactive Response System
LDH	Lactate dehydrogenase
LLN	Lower limit of normal
MCH	Mean corpuscular hemoglobin
MCHC	Mean corpuscular hemoglobin concentration
MCV	Mean corpuscular volume
MedDRA	Medical dictionary for regulatory activities
MMF	Mycophenolate mofetil
MRC	Medical Research Council
MSDS	Material safety data sheet
NAb	Neutralizing Antibody
NAFLD	Non-alcoholic fatty liver disease
NSAID	Non-steroidal anti-inflammatory agents
PD	Pharmacodynamic
PE	Plasma exchange
PK	Pharmacokinetic
RBC	Red blood cell
SAE	Serious adverse event
SAP	Statistical analysis plan
SC	Subcutaneous
SD	Standard deviation
SUSAR	Suspected unexpected serious adverse reactions
TB	Tuberculosis
TBL	Total bilirubin
ULN	Upper limit of normal
WAIHA	Warm autoimmune hemolytic anemia
WBC	White blood cell
WHO-DDE	World health organization drug dictionary enhanced

Trademark Information

Trademarks of Immunovant Sciences GmbH

Trademarks not owned by Immunovant Sciences GmbH
WinNonlin
SAS
FlowJo
nSolver

15.2. Appendix 2: Liver Laboratory Trigger and Liver Event Definitions and Follow-up Requirements

Table 4: Definitions of liver laboratory triggers and liver events

	Definition/ threshold
LIVER LABORATORY TRIGGERS	
 • ALT / AST 3x to ≤ 5x ULN • TBL 1.5x to ≤ 2 x ULN
LIVER EVENTS	
 • ALT or AST > 5 × ULN • ALP > 2 × ULN (in the absence of known bone pathology) • TBL > 2 × ULN (in the absence of known Gilbert syndrome) • ALT or AST > 3 × ULN and INR > 1.5 • Potential Hy’s Law cases (defined as ALT or AST > 3 × ULN and TBL > 2 × ULN [mainly conjugated fraction] without notable increase in ALP to > 2 × ULN) • Any clinical event of jaundice (or equivalent term) • ALT or AST > 3 × ULN accompanied by (general) malaise, fatigue, abdominal pain, nausea, or vomiting, or rash with eosinophilia • Any adverse event potentially indicative of a liver toxicity*

**These events include: hepatic failure, fibrosis, cirrhosis, and other liver damage-related conditions; non-infectious hepatitis; benign, malignant and unspecified liver neoplasms*

TBL: total bilirubin; ULN: upper limit of normal

Table 5: Follow up requirements for liver laboratory triggers and liver events

[figure not shown]
Criterion	Actions required	Follow-up monitoring
Potential Hy’s Law case^a	
 • Discontinue the study treatment immediately • Hospitalize, if clinically appropriate • Establish causality • Record the AE and contributing factors (e.g., conmeds, med hx, lab) in the appropriate CRF 	ALT, AST, TBL, Alb, PT/INR, ALP and GGT until resolution^c (frequency at investigator discretion)
ALT or AST		
> 8 × ULN	
 • Discontinue the study treatment immediately • Hospitalize if clinically appropriate • Establish causality • Record the AE and contributing factors (e.g., conmeds, med hx, lab) in the appropriate CRF 	ALT, AST, TBL, Alb, PT/INR, ALP and GGT until resolution^c (frequency at investigator discretion)
> 3 × ULN and INR > 1.5	
 • Discontinue the study treatment immediately • Hospitalize, if clinically appropriate • Establish causality • Record the AE and contributing factors (e.g., conmeds, med hx, lab) 	ALT, AST, TBL, Alb, PT/INR, ALP and GGT until resolution^c (frequency at investigator discretion)

[figure not shown]
Criterion	Actions required	Follow-up monitoring
	in the appropriate CRF	
$> 5 \text{ to } \leq 8 \times \text{ULN}$	
 Repeat LFT within 48 hours If elevation persists, continue follow-up monitoring If elevation persists for more than 2 weeks, discontinue the study drug Establish causality Record the AE and contributing factors (e.g., conmeds, med hx, lab) in the appropriate CRF 	ALT, AST, TBL, Alb, PT/INR, ALP and GGT until resolution^c (frequency at investigator discretion)
$> 3 \times \text{ULN}$ accompanied by symptoms^b	
 Discontinue the study treatment immediately Hospitalize if clinically appropriate Establish causality Record the AE and contributing factors (e.g., conmeds, med hx, lab) in the appropriate CRF 	ALT, AST, TBL, Alb, PT/INR, ALP and GGT until resolution^c (frequency at investigator discretion)
$> 3 \text{ to } \leq 5 \times \text{ULN}$ (subject is asymptomatic)	
 Repeat LFT within the next week If elevation is confirmed, initiate close observation of the subject 	Investigator discretion Monitor LFT within 1 to 4 weeks
ALP (isolated)		
$> 2 \times \text{ULN}$ (in the absence of known bone pathology)	
 Repeat LFT within 48 hours If elevation persists, establish causality Record the AE and contributing factors (e.g., conmeds, med hx, lab) in the appropriate CRF 	Investigator discretion Monitor LFT within 1 to 4 weeks or at next visit
TBL (isolated)		
$> 2 \times \text{ULN}$ (in the absence of known Gilbert syndrome)	
 Repeat LFT within 48 hours If elevation persists, discontinue the study drug immediately Hospitalize if clinically appropriate Establish causality Record the AE and contributing factors (e.g., conmeds, med hx, lab) in the appropriate CRF 	ALT, AST, TBL, Alb, PT/INR, ALP and GGT until resolution^c (frequency at investigator discretion) Test for hemolysis (e.g., reticulocytes, haptoglobin, unconjugated [indirect] bilirubin)
$> 1.5 \text{ to } \leq 2 \times \text{ULN}$ (subject is asymptomatic)	
 Repeat LFT within the next week If elevation is confirmed, initiate close observation of the subject 	Investigator discretion Monitor LFT within 1 to 4 weeks or at next visit
Jaundice	
 Discontinue the study treatment immediately Hospitalize the subject Establish causality Record the AE and contributing factors (e.g., conmeds, med hx, lab) in the appropriate CRF 	ALT, AST, TBL, Alb, PT/INR, ALP and GGT until resolution^c (frequency at investigator discretion)
Any AE potentially indicative of a liver	
 Consider study treatment interruption or discontinuation Hospitalization if clinically 	Investigator discretion

[figure not shown]
Criterion	Actions required	Follow-up monitoring
toxicity*	appropriate 
 • Establish causality • Record the AE and contributing factors (e.g., conmeds, med hx, lab) in the appropriate CRF 	

[figure not shown]
Elevated ALT/AST > 3 × ULN and TBL > 2 × ULN but without notable increase in ALP to > 2 × ULN^b(General) malaise, fatigue, abdominal pain, nausea, or vomiting, or rash with eosinophilia^cResolution is defined as one of the following: (1) return to baseline values, (2) stable values at three subsequent monitoring visits at least 2 weeks apart, (3) remain at elevated level after a maximum of 6 months, (4) liver transplantation, and (5) death.

At the investigator’s discretion, investigation(s) for contributing factors to the liver event may include: serology tests, imaging, pathology assessments, hepatologist consultation; obtaining more detailed history of symptoms and prior or concurrent diseases, history of concomitant drug use, and exclusion of underlying liver disease.

[Redacted]

[Redacted]

[Redacted]

[Redacted]

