6.8. Safety Management Criteria for Individual Participants

6.8.1. Liver Chemistry Management Criteria

To ensure subject safety and enhance reliability in determining the hepatotoxic potential of an investigational drug, a standardized process for identification, monitoring and evaluation of liver events is to be followed.

The following two categories of abnormalities / adverse events are to be considered during the course of the study (irrespective of whether classified/reported as an AE or SAE):

1. Liver laboratory triggers. These require repeated assessments of the abnormal laboratory parameter
2. Liver events. These require close observation and follow-up monitoring. Contributing factors are to be recorded on the appropriate CRF(s).

Please refer to Appendix 2 Table 4 for complete definitions of liver laboratory triggers and liver events. Every liver event defined in Appendix 2 Table 5 to be followed up by the investigator or designated personnel at the trial site, as summarized below. Additionally, required actions in case of liver laboratory triggers and liver events are outlined in Appendix 2, Table 5 (Follow up requirements for liver laboratory triggers and liver events). Repeat liver chemistry tests (i.e. ALT, AST, TBL, PT/INR, ALP and G-GT) regularly to confirm elevation and follow trends.

The following additional follow up should also be considered:

- Obtain a more detailed history of symptoms and prior or concurrent diseases.
- Obtain a history of concomitant drug use (including non-prescription medications and herbal and dietary supplement preparations), alcohol use, recreational drug use, and special diets.
- Exclude causes of underlying liver disease, as specified in Section 6.3 Exclusion Criteria
- Perform imaging such as abdominal US, CT or MRI, as appropriate
- Obtain a history of exposure to environmental chemical agents.
- Consider gastroenterology or hepatology consultations.

All follow-up information and procedures performed must be recorded as appropriate in the CRF.

These liver chemistry repeats will be performed using the central laboratory. If results will not be available from the central laboratory, then the repeats can also be performed at a local laboratory to monitor the safety of the subject. If a liver event is subsequently reported, any local liver chemistry tests previously conducted that are associated with this event should have results recorded on the appropriate CRF.

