6.9. Toxicity Management Criteria

6.9.1. Toxicity Management Criteria (AEs, Cardiovascular, and Injection Site Reactions)

The severity of each AE will be graded and managed according to the criteria in Table 2 (CTCAE version 5.0). Study drug should be permanently discontinued for any grade 4 toxicity other than hemoglobin decrease. Management of hemoglobin < 7.0 g/dL or anemia in the presence of cardiovascular symptoms is described in section 6.9.2. For grade 3 TEAE not considered related to WAIHA signs/symptoms, study drug should be withheld. Study drug may only be restarted following a grade 3 TEAE after discussion with the medical monitor. Table 2 Criteria for Determining the Grade/Severity of Adverse Event Terms

Grade	Criteria
1/Mild	Asymptomatic or mild symptoms, clinical or diagnostic observations only; intervention not indicated
2/Moderate	Limiting age-appropriate instrumental activities of daily living; minimal, local, or noninvasive intervention as indicated
3/Severe or medically significant	Not immediately life-threatening; hospitalization or prolongation of hospitalization indicated; disabling; limiting self-care activities of daily living, intervention as indicated
4/Life-threatening	Life threatening consequences; urgent intervention indicated
5/Death	Death related to adverse event

Injection Site Reactions

Injection site evaluations will be made by clinical staff following administration of RVT-1401 as described below. Additional details related to the specific injection site location will be included within a study specific manual. If an injection site reaction is observed, a physician will characterize and document the reaction as an AE. Review of the injection site will continue until the AE is resolved. Symptomatic treatment (e.g., warm compresses, topical steroids, antihistamines if itching is present, or NSAIDs) may be provided for injection site reactions at the discretion of the Investigator.

The injection sites will be monitored for pain, tenderness, erythema and swelling. Each injection site reaction will be categorized using the intensity grading scheme presented in Table 3.

Table 3 Criteria for Determining the Grade/Severity of Injection Site Reactions

Grade	Criteria
1/Mild	Tenderness with or without associated symptoms (e.g., warmth, erythema, itching)
2/Moderate	Pain; lipodystrophy; edema; phlebitis
3/Severe or medically significant	Ulceration or necrosis; severe tissue damage; operative intervention indicated

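### The bilirubin and jaundice stopping rules in Protocol Appendix 2, Table 5 make no allowance for hemolysis, so WAIHA itself can force a liver stop

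*Protocol*

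**What the plan says.** Protocol 6.8.1 gives Table 5 binding force: "required actions in case of liver laboratory triggers and liver events are outlined in Appendix 2, Table 5". It applies "irrespective of whether classified/reported as an AE or SAE".

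- **Isolated total bilirubin (TBL) above 2 × ULN.** Liver tests are repeated within 48 hours; then "If elevation persists, discontinue the study drug immediately", and "Hospitalize if clinically appropriate". Known Gilbert syndrome is the only exemption. The follow-up column adds "Test for hemolysis (e.g., reticulocytes, haptoglobin, unconjugated [indirect] bilirubin", but no action depends on the result.
- **Jaundice.** The row opens "Discontinue the study treatment immediately Hospitalize the subject". It has no repeat, no hemolysis test and no exemption. Table 4 counts clinical jaundice of any cause.

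In both rows, establishing causality is listed after the stop and is not a condition of it. Neither row has a restart route.

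The general toxicity rules in 6.9.1 do make room for the disease: "Study drug should be permanently discontinued for any grade 4 toxicity other than hemoglobin decrease", and "For grade 3 TEAE not considered related to WAIHA signs/symptoms, study drug should be withheld". After a grade 3 hold, restart is possible once the medical monitor has been consulted.

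**The concern.** In most trials a bilirubin above 2 × ULN points toward the liver. In WAIHA it may simply reflect red-cell destruction, which is what the drug is meant to reduce; bilirubin is itself a secondary efficacy measure here, beside LDH and haptoglobin. A stop that ignores the source of the bilirubin can withdraw drug because the disease is active.

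Two things are at stake. A participant may lose treatment with no evidence of hepatic harm. And because 11.2 counts an admission of any length toward seriousness, the jaundice row can create an SAE by rule rather than by clinical need.

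**Working it through.** The plan states no figure to reproduce, so the check is a reading of the rules against the disease and entry criteria, plus simple counts.

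**1. Can WAIHA meet the two rows?**
- Section 3.2 lists raised unconjugated bilirubin among common laboratory findings.
- Inclusions 6 and 7 require haptoglobin below LLN, LDH above ULN and hemoglobin below 10 g/dL, so participants enter with laboratory signs of hemolysis.
- No numeric bilirubin limit applies at entry. Exclusion 10 leaves laboratory abnormalities to the investigator's opinion.
- The TBL limit is a multiple of ULN, not of baseline. A participant could enter above 2 × ULN and meet the row without any change.

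**2. Does the 48-hour repeat protect against this?** It removes a transient rise, not continuing hemolysis. Section 3.3.2 expects the lowest IgG by the 3rd to 5th weekly dose. Days after the first dose = 7 × (dose number − 1): 7 × 2 = 14 for the 3rd dose and 7 × 4 = 28 for the 5th. A 2-day repeat early in treatment falls well before the full drug effect is expected.

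**3. Counts from Table 5.**

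| Row | Discontinuation required | Admission |
|---|---|---|
| Potential Hy's law | yes | if appropriate |
| ALT/AST > 8 × ULN | yes | if appropriate |
| ALT/AST > 3 × ULN with INR > 1.5 | yes | if appropriate |
| ALT/AST > 5 to ≤ 8 × ULN | yes, if it lasts over 2 weeks | not mentioned |
| ALT/AST > 3 × ULN with symptoms | yes | if appropriate |
| TBL > 2 × ULN | yes, if it persists | if appropriate |
| Jaundice | yes | unqualified |
| AE suggesting liver toxicity | to be considered | if appropriate |

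Seven rows require discontinuation, and two of them (TBL, jaundice) can be met with normal ALT and AST. Seven rows mention admission: six leave it to clinical judgment, potential Hy's law among them, and only jaundice does not.

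**4. Are those two the only exposed rows?** Probably not.
- Section 3.2 also lists AST raised out of proportion to ALT. The row for ALT/AST above 3 × ULN with symptoms counts fatigue as a symptom. Inclusion 7 requires symptoms of anemia and gives fatigue as an example. Exclusion 9 admits a raised AST when liver imaging is acceptable and sets no upper limit.
- Table 4 limits the Hy's law bilirubin criterion to a mainly conjugated rise. The Table 5 footnote restates the criterion without that limit, so an unconjugated rise with AST above 3 × ULN would meet it.

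Two of seven is therefore the number that bilirubin or jaundice alone can trigger, not the total that WAIHA could trigger.

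**5. Do other sections rescue the rule?** No. The WAIHA exception in 6.9.1 concerns the grade 3 hold, while 6.8.1 applies Table 5 whatever the AE classification. Section 8 bars waivers except for immediate safety concerns. The permissive wording in 6.7.1 concerns withdrawal from the study, not the drug stop.

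**The case against.** A cautious liver stop is defensible. The completed repeat-dose experience described is 8 + 8 = 16 healthy subjects given up to four weekly doses. The TBL row does show awareness of hemolysis, and a raised bilirubin in section 3.2 need not exceed 2 × ULN. The comparison with 6.9.1 also has limits: its grade 4 exception covers only a fall in hemoglobin, so the protocol does not exempt disease effects generally. All of this stands. It limits the weight of the point but does not make the hemolysis result count for anything.

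A rule that relied on hemolysis markers would discriminate poorly. Low haptoglobin is required at entry and reticulocytosis is a common WAIHA finding, so both would often be abnormal whatever the liver is doing. This stands too, and it is why the fix rests on direct bilirubin and comparison with baseline.

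On SAEs, 11.2 already covers admission for urgent transfusion or for symptoms of recurring WAIHA. That answers cases where admission is needed; it does not answer an admission ordered by the table alone.

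A reader might go further and infer a biased primary endpoint. The documents do not support that. Table 5 stops drug, not participation; withdrawal under 6.7.1 is discretionary, and 6.1 allows replacement. Only a participant without a Week 13 hemoglobin would drop out of the available-data analysis in 10.3.2. SAP version 3.0 provides only listings for the five Cohort 1 subjects.

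**Conclusion.** The point holds as a flaw in the stopping rule: WAIHA can trigger a required discontinuation without liver injury, through two rows on bilirubin or jaundice alone and possibly through others that involve AST. The jaundice row also mandates an admission that the table leaves to judgment even for a potential Hy's law case.

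Its practical size is unknown. A reader might infer that such stops would be common, but the documents give no bilirubin levels and no jaundice rate, and section 3.2 does not name jaundice. Nor can the one early termination after Week 3 reported in the SAP introduction be attributed to this rule, since no reason is given there.

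The conclusion assumes that sites follow Table 5 as written and that the blacked-out lines after the table contain no exemption. The SAP reports that the study was paused, with five subjects enrolled, because of a lipid effect. The change therefore matters only if dosing resumes or the table is carried into another protocol.

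**What to change.** 1. **Isolated-TBL and jaundice rows.** Hold drug, add direct bilirubin to the repeat liver panel and compare with baseline. Discontinue if the rise is mainly conjugated or is not explained by hemolysis. Otherwise allow restart after discussion with the medical monitor, as 6.9.1 does after a grade 3 event. Do not let haptoglobin or reticulocytes alone decide. State the cut-off for a mainly conjugated rise, since Table 4 gives none.
2. **Jaundice row.** Add the hemolysis test and replace the unqualified admission with "Hospitalize if clinically appropriate".
3. **Hy's law footnote to Table 5.** Add Table 4's restriction to a mainly conjugated rise.

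Leave the ALT/AST and INR thresholds as they are. The exposure of the row for ALT/AST above 3 × ULN with symptoms should be recognised, but those enzymes are direct liver signals and I would not relax them here.

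**Cost.** In mixed cases permanent discontinuation comes slightly later, although no drug is given while the cause is open. Direct bilirubin is already in the scheduled chemistry (8.3.4) but not in the repeat panel of 6.8.1, and chemistry is not scheduled at Weeks 6, 8, 10 or 12, so some unscheduled draws may be needed. Because a safety stop changes, a protocol amendment with IRB/IEC approval is required before use (13.1.2), and re-consent if the change is judged to alter risk substantially (13.1.3).
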